#### **7.3.3. Withdrawal of informed consent**

Subjects may voluntarily withdraw consent to participate in the study for any reason at any time. Withdrawal of consent occurs only when a subject:

- Does not want to participate in the study anymore,
- AND
- Does not allow further collection of personal data.

It is encouraged that the subject provides withdrawal of consent in writing.

In this situation, the Investigator should make a reasonable effort (eg, telephone call, e-mail, letter) to understand the primary reason for the subject's decision to withdraw his/her consent and record this information. The subject's vital status can be verified upon contact with subject's primary care physician or other sources according to local rules and regulations.

No further assessments must be conducted, and the data that would have been collected at subsequent visits will be considered missing.

Further attempts to contact the subject are not allowed unless safety findings require communication or follow-up.

All efforts should be made to complete the assessments prior to study withdrawal. A final evaluation at the time of the subject's study withdrawal should be made as detailed in the assessment table (Table 2).

The Sponsor will continue to keep and use collected study information (including any data resulting from the analysis of a subject's samples until the time of withdrawal) according to applicable law.

All biological samples not yet analyzed at the time of withdrawal may still be used for further testing/analysis in accordance with the terms of this protocol and the informed consent form and with local rules and regulations.

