#### Cohort 1 (Non-ventilated Subjects)

1. Mortality rate at Day 29
2. Ventilation free survival (Time to ventilation or death) by Day 29

Defined as time from randomization to ventilation or death; subjects still alive will be censored at Day 29.

3. Overall survival by Day 29

Defined as time from randomization to death; subjects still alive will be censored at Day 29.

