### **4.4. Methods for Handling Missing Data**

For efficacy data, missing NIAID scale and survival status at target days will be handled per Section 5.7.2.

For safety data, refer to Section 8.1 for detailed date imputation guidelines.

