In calculation of the mortality rate, a subject with the last known alive date on or after the target day is considered alive. If the last known alive date is before the target day but within their visit window, the subject is considered alive at the target day. Subjects terminated the study early will be considered alive since all subjects in the study are hospitalized and early termination other than due to death mostly happens to subjects improved or discharged.

Sensitivity analyses may be conducted to assess missing data assumptions for the primary endpoint and the mortality rate at Day 29. Two methods might be considered:

- 1) Multiple imputation approach with a covariate of discharge status at last assessment, adjusting for randomization strata.
- 2) Tipping point analyses. The goal is to explore the plausibility of missing data assumptions under which the conclusions change, i.e., under which there is no longer evidence of efficacy.

We plan to extend tipping points for binary data (Yan et al., 2009) to binary data with stratification. Let  $n_{1m}$  and  $n_{0m}$  be the number of missing values in the treatment and placebo arms respectively. When there is no stratification, the responders (Let  $r_{1m}$  and  $r_{0m}$  to denote the numbers) among the  $n_{1m}$  and  $n_{0m}$  subjects can range from 0 to  $n_{1m}$  and  $n_{0m}$ , respectively, by adding 1 responder at a time. A heat map plot can be drawn for assessment.

In our study when stratification exists, multiple imputation might be needed in extending Yan et al's approach. Repeat the following algorithm for each combination of  $r_{1m}$  and  $r_{0m}$ , where  $r_{1m} = 0, \dots, n_{1m}$  and  $r_{0m} = 0, \dots, n_{0m}$ , 1), and draw a heat map plot using data obtained.

- 1) Randomly select  $r_{1m}$  and  $r_{0m}$  subjects as responders and the rest as the non-responders.
- 2) Include the responders from step 1) in the observed responders without missing data, calculate the approximately normally distributed CMH test statistic instead of the usual Chi-square distributed CMH test statistic.
- 3) Repeat Step 1 and Step 2 a fixed number of times, e.g. 200. The statistics obtained are passed to PROC MIANALYZE to perform a combined CMH test to obtain a p-value.

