### 5.7.3. Censoring Rules for Time to Event Endpoints

NIAID scores collected within visit windows (described in Section 4.3) of the target days will be used for time to event analysis by the corresponding target day. The last assessments referred to in this section include those occur after the target day but within the protocol-defined visit window. For example, if a subject has not had 2-point clinical improvement by Day 29 visit, which occurs on Day 30, the subject will be censored at Day 30 instead of Day 22 (the last assessment before Day 29).

For favorable time to event endpoints, death before the target date Day X (X=15, 29, or 90) will be censored at Day 19 for X = 15, and Day 35 for X = 29 unless otherwise specified. Details are below.

- Time to ventilation or death (Ventilation free survival) by Day 29  
Defined as time (in days) from randomization to the date of death or start date of using mechanical ventilation (NIAID  $\leq 2$ ) by Day 29 for Cohort 1. All subjects who have never had

NIAID  $\leq 2$  by Day 29 will be censored at the last assessment date of NIAID 8-point ordinal scale.

- [REDACTED]  
[REDACTED]  
[REDACTED]  
[REDACTED]  
[REDACTED]
- Overall survival by Day X (X=29, or [REDACTED])  
Defined as time (in days) from the randomization date to the date of death by Day X. All survival subjects will be censored at last date known alive on/before Day X.
- [REDACTED]  
[REDACTED]  
[REDACTED]  
[REDACTED]  
[REDACTED]  
[REDACTED]
- Time to K-point clinical improvement by Day X (K=1, or [REDACTED], X=[REDACTED], or 29)  
Defined as time (in days) from randomization to the date of a K-point improvement on the NIAID 8-point ordinal scale, or discharge from the hospital, whichever occurs first, by Day X. Alive subjects who do not have K-point improvement nor discharge from the hospital will be censored at the date of the last NIAID 8-point ordinal scale assessment on/before Day X. Dead subjects will be censored at Day 19 for Day [REDACTED] endpoint and at Day 35 for Day 29 endpoint.
- [REDACTED]  
[REDACTED]  
[REDACTED]  
[REDACTED]  
[REDACTED]  
[REDACTED]
- [REDACTED]  
[REDACTED]  
[REDACTED]  
[REDACTED]

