#### **4.4. Methods for Handling Missing Data**

For efficacy data, a survival sweep will be conducted before the database lock to minimize the amount of missing survival status data. Missing NIAID scale and survival status at target days will be handled per Section [5.7.2](#).

For safety data, refer to Section [8.1](#) for detailed date imputation guidelines.

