### **5.7.2. NIAID Scale and Missing Data Imputation for Binary Endpoints**

When two or more NIAID scores are collected on the same study day, the lowest score will be used, except at the date of discharge, in which the highest NIAID score will be used.

Baseline NIAID scores are derived from Day 1 or screening assessment:

- If screening and day 1 are the same day, and screening assessment is available, then the screening NIAID will be used as baseline.
- If screening and day 1 are not on the same day, or screening NIAID assessment is missing, the score from Day 1 will be used as baseline.

For endpoints where the event of interest is favorable, like proportion of subjects alive and free of ventilation, and proportion of subjects with 1-point/2-point clinical improvement, the following imputation rule of NIAID scale will be adopted:

- When the NIAID assessment is missing at the target day (Day 15, 29, etc.), the NIAID score closest to and within 2 days of the target day will be used. In case of ties with equal number of days on either side of target day, the value before the target day will be used.
- When no NIAID assessment is available within 3 days of the target day, the primary treatment comparison will be based on a combination of responder imputation and non-responder imputation:
  - Discharged subjects will be considered as having had the event (responders).
  - Subjects who are still in the hospital will be considered as not having had the event (non-responders).
  - Subjects who terminate the study early including death will be considered as not having had the event for all subsequent target days after discontinuation (non-responders).

In calculation of the mortality rate, a subject with the last known alive date on or after the target day is considered alive. If the last known alive date is before the target day but within 2 days of the visit window, the subject is considered alive at the target day. Since survival sweep will be conducted for each database lock, minimum missing mortality status is expected.

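### For Day 29 mortality, the Phase 3 SAP counts every subject who leaves the study early for a reason other than death as alive, whatever their last known status

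*Combined protocol and SAP*

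**What the plan says.** Protocol 10.2 lists "Mortality rate at Day 29" as the first secondary endpoint for Cohort 1. Under Phase 3 SAP 5.7.1 it is Family 2 of the confirmatory sequence.

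Phase 3 SAP 5.7.2 sets the mortality rule: "Subjects terminated the study early will be considered alive since all subjects in the study are hospitalized". The sentence goes on to give as its reason that "early termination other than due to death mostly happens to subjects improved or discharged". No condition is placed on the last NIAID score, on discharge, or on how long before Day 29 the subject was last seen.

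Three neighbouring rules differ:

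- **Primary endpoint (Phase 3 SAP 5.7.2).** A subject who terminates before the target day is a responder if the last NIAID score met the endpoint criteria. A subject with no post-randomization assessment is a non-responder.
- **Overall survival, Family 4 (Phase 3 SAP 5.7.3).** "All survival subjects will be censored at last date known alive on/before Day X".
- **Phase 2 SAP 4.4 and 5.7.2.** "a survival sweep will be conducted before the database lock to minimize the amount of missing survival status data", and then "Since survival sweep will be conducted for each database lock, minimum missing mortality status is expected". The Phase 2 mortality rule does not impute early terminators as alive.

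The Phase 3 counterpart of section 4.4 says only that "missing NIAID scale and survival status at target days will be handled per Section 5.7.2". Neither that section nor 5.7.2 mentions a sweep. Section 5.7.2 does describe multiple imputation and a tipping-point analysis covering Day 29 mortality, but introduces both in permissive terms.

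**The concern.** A formally tested mortality comparison should rest on ascertained vital status, or on an assumption tied to what was last known about the subject. Here it rests on a blanket favourable assumption. The word *mostly* in the stated reason concedes exceptions, and the rule covers those too. Discharge is not among the reasons for early discontinuation in Phase 3 SAP 5.2, which include withdrawal, loss to follow-up, physician decision and site termination. Discharged subjects stay in follow-up by telephone. It is therefore not evident that the subjects caught by the rule are the low-risk ones.

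A death after an in-hospital withdrawal, if nobody checks for it, enters the analysis as a survival. Each arm's observed death rate can only fall or stay the same. If such deaths are unevenly spread across arms, the test of the endpoint most likely to be read as a survival claim is distorted.

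**Working it through.** **1. One subject under three rules.** All three apply when vital status at Day 29 is unknown and the subject ended the study early for a reason other than death.

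| Last known status | Primary endpoint (Family 1) | Day 29 mortality (Family 2) | Overall survival (Family 4) |
|---|---|---|---|
| On invasive ventilation (NIAID 2) | non-responder, by implication | alive | censored when last known alive |
| No post-randomization assessment | non-responder | alive | censored when last known alive |
| Discharged | responder | alive | censored when last known alive |

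The second row takes the unfavourable assumption in Family 1 and the favourable one in Family 2.

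**2. The plan's own figure.** The SAP states no Cohort 1 mortality rate and no power for Family 2. Its primary-endpoint power does reproduce. With 87.5% against 74.4%, 200 per arm and two-sided 0.05, the pooled chi-square approximation is Φ[(d − 1.96·SE0)/SE1], where d = 0.131, SE0 = 0.0393 and SE1 = 0.0387. The result is 91.9%, against a stated minimum of 90%. The mortality rule does not affect this figure.

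**3. True null with unevenly hidden deaths.** The arm size is 581/3 ≈ 194, from the enrolment count in Phase 3 SAP 1.4. Mortality p and the net number k of hidden deaths in one active arm are assumptions. The observed rates are p and p − k/194. Two-sided rejection is Φ[(d − 1.96·SE0)/SE1] + Φ[(−d − 1.96·SE0)/SE1], with d = k/194.

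For p = 15% and k = 4: d = 0.0206, SE0 = 0.0352 and SE1 = 0.0352. The two tails are 8.5% and 0.5%, which sum to 9.0%.

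| k | Shift (points) | p = 10% | p = 15% | p = 20% | p = 25% |
|---|---|---|---|---|---|
| 0 | 0 | 5.0% | 5.0% | 5.0% | 5.0% |
| 2 | 1.0 | 6.4% | 6.0% | 5.8% | 5.6% |
| 4 | 2.1 | 10.9% | 9.0% | 8.1% | 7.6% |
| 8 | 4.1 | 32.3% | 22.7% | 18.5% | 16.2% |

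For scale, 15% of 194 is about 29 deaths, so 2, 4 and 8 hidden deaths are 7%, 14% and 27% of an arm's deaths. The formula is symmetric. The same excess hidden in placebo gives the same rejection rates, with the error then falling mainly against the drug.

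**4. A true effect with hidden deaths.** Assume 20% placebo and 10% active mortality, 194 per arm, and the same power formula.

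| Share of deaths hidden (placebo / active) | Observed rates | Risk difference (points) | Power |
|---|---|---|---|
| 0 / 0 | 20.0% / 10.0% | 10.0 | 79% |
| 5% / 5% | 19.0% / 9.5% | 9.5 | 77% |
| 10% / 10% | 18.0% / 9.0% | 9.0 | 74% |
| 20% / 20% | 16.0% / 8.0% | 8.0 | 68% |
| 0 / 20% | 20.0% / 8.0% | 12.0 | 93% |
| 20% / 0 | 16.0% / 10.0% | 6.0 | 42% |

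Equal proportional loss leaves the risk ratio unchanged and shrinks the difference.

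**5. Family 2 rule against Family 4 rule.** Assume 20% true mortality, a constant hazard, and a fraction m leaving at a uniformly distributed time for reasons unrelated to risk. The alive rule estimates (1 − m)·0.20 + m·[1 − 0.20/(−ln 0.80)] = (1 − m)·0.20 + m·0.1037. For m = 2%, 5% and 10% this gives 19.8%, 19.5% and 19.0%. Kaplan-Meier with censoring gives 20.0% in each case.

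All test figures are unstratified, pairwise approximations, whereas the plan uses a stratified CMH test. They are also unconditional. Family 2 is reached only if both doses have p ≤ 0.05 in Family 1, and it is then tested by Hochberg, so these are not familywise error rates.

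**The case against.** The documents contain real safeguards. The schedule of activities requires survival assessment at Days 15, 22, 29, 60 and 90, and by telephone at Days 15, 22 and 29 after discharge. Protocol 7.3.4 does not allow a subject to be classed as lost to follow-up until the end of the study, after documented due diligence. Phase 3 SAP 5.7.5.2 allows a supportive mortality estimate from overall survival, which avoids the imputed-alive rule. Section 5.7.2 sets out a step-by-step tipping-point algorithm, and the SAP history records that the sensitivity analyses were added or detailed after regulatory feedback. All of this stands, and it may leave few subjects with unknown status. It does not change the formally tested analysis, and the sensitivity analyses remain optional.

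A reader might infer more than the text supports:

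- **That deaths are counted as alive.** The stated reason confines the rule to terminations other than death.
- **That the rationale contradicts itself.** Everyone is hospitalized at entry and may later be discharged. The sentence is clumsy, not contradictory.
- **That the rule favours the drug.** That requires more hidden deaths in an active arm than in placebo, and the documents give no termination or death counts by arm. Even assuming 6% against 3% in-hospital termination with 30% mortality among them, the net is 194 × 0.03 × 0.30 ≈ 1.7 deaths per arm. Two-sided rejection is then about 5.7%, and reversing the split reverses the direction.
- **That the overall-survival rule contradicts it.** The two are different missing-data assumptions for two estimators. They are inconsistent and can give different Day 29 rates, but they are not logically incompatible.
- **That vital-status checks were abandoned.** Silence shows only that the Phase 3 SAP does not specify a sweep.
- **That the 15% dropout allowance measures the problem.** It is a Phase 2 Cohort 1 planning figure, not a Phase 3 rate of unknown vital status.

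**Conclusion.** The concern holds as a defect in a stated rule. The Phase 3 SAP imputes all non-death early terminators as alive for a confirmatory endpoint, without regard to last NIAID score or discharge. This departs from the SAP's own handling of the primary endpoint and of overall survival, and it comes without the survival sweep that the Phase 2 SAP specified.

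The rule can lower the observed death rate in each arm, and it can distort the comparison in either direction. The documents fix neither direction nor size. On the assumed inputs above, a net 2 hidden deaths in one arm matter little (about 6% rejection at 15% mortality), 4 matter somewhat (9%) and 8 matter a great deal (23%). Equal proportional loss is conservative for the risk difference. The change should be made before database lock. It is not a finding that the mortality result is biased.

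**What to change.** 1. **Phase 3 SAP 4.4.** Restore a survival sweep before each database lock. Protocol 7.3.3 supports it: "The subject's vital status can be verified upon contact with subject's primary care physician or other sources", subject to local rules. For subjects who withdrew consent, use those outside sources and do not re-contact the subject, which 7.3.3 bars unless safety findings require it.
2. **Phase 3 SAP 5.7.2.** State that a recorded death counts as a death whatever the termination reason. Limit the imputed-alive rule to subjects known alive in or after the Day 29 window, or last known to be discharged. Do not automatically count in-hospital terminators with unknown status as alive, and specify before lock how they are handled. Treating discharged subjects as alive is still an assumption, which item 3 tests.
3. **Reporting and sensitivity.** Tabulate unknown Day 29 vital status by arm, with last known status and reason for termination. Make the multiple-imputation and tipping-point analyses already described mandatory for Day 29 mortality.

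The cost is a limited number of record checks, a few sentences of SAP text and a little more programming. No change to enrolment, visits or treatment is needed.

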### 5.7.3. Censoring Rules for Time to Event Endpoints

NIAID scores collected within visit windows (described in Section 4.3) of the target days will be used for time to event analysis by the corresponding target day. The last assessments referred to in this section include those occur after the target day but within the protocol-defined visit window. For example, if a subject has not had 2-point clinical improvement by Day 29 visit, which occurs on Day 30, the subject will be censored at Day 30 instead of Day 22 (the last assessment before Day 29).

For favorable time to event endpoints, death before the target date Day X (X=15, 29, or 90) will be censored at Day 19 for X = 15, and Day 35 for X = 29 unless otherwise specified. Details are below.

- Time to ventilation or death (Ventilation free survival) by Day 29  
Defined as time (in days) from randomization to the date of death or start date of using mechanical ventilation (NIAID  $\leq 2$ ) by Day 29 for Cohort 1. All subjects who have never had

NIAID  $\leq 2$  by Day 29 will be censored at the last assessment date of NIAID 8-point ordinal scale.

- [REDACTED]  
[REDACTED]  
[REDACTED]  
[REDACTED]  
[REDACTED]
- Overall survival by Day X (X=29, or [REDACTED])  
Defined as time (in days) from the randomization date to the date of death by Day X. All survival subjects will be censored at last date known alive on/before Day X.
- [REDACTED]  
[REDACTED]  
[REDACTED]  
[REDACTED]  
[REDACTED]  
[REDACTED]
- Time to K-point clinical improvement by Day X (K=1, or [REDACTED], X=[REDACTED], or 29)  
Defined as time (in days) from randomization to the date of a K-point improvement on the NIAID 8-point ordinal scale, or discharge from the hospital, whichever occurs first, by Day X. Alive subjects who do not have K-point improvement nor discharge from the hospital will be censored at the date of the last NIAID 8-point ordinal scale assessment on/before Day X. Dead subjects will be censored at Day 19 for Day [REDACTED] endpoint and at Day 35 for Day 29 endpoint.
- [REDACTED]  
[REDACTED]  
[REDACTED]  
[REDACTED]  
[REDACTED]  
[REDACTED]
- [REDACTED]  
[REDACTED]  
[REDACTED]  
[REDACTED]

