#### **4.2.4. Last Contact**

Last contact or last date known alive is defined as the last non-imputed date of any subject record prior to or on the data cut-off date in the clinical database.

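### Phase 3 overall survival: read literally, the SAP's censoring sentence discards an in-window contact after Day 29 that shows the subject was alive, and it should be aligned with the protocol (minor)

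*Combined protocol and SAP*

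**What the plan says.** Protocol 10.2, Cohort 1, gives overall survival by Day 29 as the third secondary endpoint: "Defined as time from randomization to death; subjects still alive will be censored at Day 29".

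Phase 3 SAP 5.7.3 words it differently: "All survival subjects will be censored at last date known alive on/before Day X". SAP 4.2.4 supplies the date, looking back from the data cut-off: "Last contact or last date known alive is defined as the last non-imputed date of any subject record".

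The opening paragraph of SAP 5.7.3 has a window provision: "The last assessments referred to in this section include those occur after the target day but within the protocol-defined visit window". Its example is a subject without 2-point improvement whose Day 29 visit takes place on Day 30. That subject is censored at Day 30, not Day 22.

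For the binary mortality rate, SAP 5.7.2 states that "a subject with the last known alive date on or after the target day is considered alive".

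After discharge, survival is checked by telephone at Days 15, 22 and 29 (protocol Schedule of Activities, footnote 13). The current protocol window for Day 29 is +4 days. SAP 4.3 uses -2 to +4 for Day 29 endpoints so as to cover all protocol versions.

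**The concern.** Four of the five days in the current protocol window (Days 29 to 33) fall after Day 29. A contact on one of those days is in window and shows that the subject was alive at Day 29. Taken literally, the overall-survival sentence cannot use it, because the contact is not on or before Day 29.

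The loss is one-sided. If a Day 31 call reveals a death on Day 26, the death counts as an event. If the same call finds the subject alive, the information is dropped and follow-up stops at an earlier record. Censoring then depends on the outcome, which Kaplan-Meier and the log-rank test assume it does not. The subjects removed are discharged survivors, so each death on Days 23 to 29 is counted against too small a risk set.

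Overall survival is Family 4 of the confirmatory sequence (SAP 5.7.1). SAP 5.7.5.2 also allows the mortality rate to be estimated from it as a supportive analysis. That supportive figure could differ from the main mortality rate purely because of the censoring rule.

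**Working it through.** **The passages applied to one record.** Assume a subject discharged on Day 9, with calls on Days 15, 22 and 31, alive at each, and no other dated record after Day 22.

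| Rule | Result |
|---|---|
| Protocol 10.2, overall survival | censored at Day 29 |
| SAP 5.7.2, binary mortality | alive at Day 29 |
| SAP 5.7.3, ventilation-free survival, with the window provision | censored at Day 31 |
| SAP 5.7.3, overall survival, literal | censored at Day 22 |
| SAP 5.7.3, overall survival, date capped at Day X | censored at Day 29 |
| SAP 5.7.3, overall survival, if the window provision is extended to it | censored at Day 31 |

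Three censoring days are arguable for one endpoint. On the literal reading the subject is followed to Day 31 for ventilation or death but only to Day 22 for death.

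**Size under the literal reading.** The documents give no overall-survival or mortality figure for Phase 3 Cohort 1, so there is nothing to reproduce. The arm size is 581/3, about 194 (SAP 1.4). All other counts are assumed: 28 deaths by Day 22, 3 deaths on Days 23 to 29, and 109 discharged survivors whose Day 29 call falls on Days 30 to 33.

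1. At risk after Day 22, with survivors censored at Day 29: 194 - 28 = 166.
2. Mortality with censoring at Day 29: 1 - (166/194) x (163/166) = 31/194 = 16.0%.
3. At risk after Day 22 on the literal rule: 166 - 109 = 57.
4. Mortality on the literal rule: 1 - (166/194) x (54/57) = 1 - 0.8557 x 0.9474 = 18.9%.
5. Excess: 18.94 - 15.98 = 3.0 percentage points.

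In general, with N in the arm, A alive after Day 22, c censored early and d deaths on Days 23 to 29, the excess is (d/N) x c/(A - c). Here it is (3/194) x (109/57) = 0.0296. It is zero when d = 0 or c = 0.

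**Range, all inputs assumed.** With 70% of the arm discharged, 80% of those called after Day 29, Day 29 mortality of 8% to 20% and 5% to 15% of deaths on Days 23 to 29, the excess is 0.6 to 6.2 points. With 60% to 70% discharged and 50% to 100% called late, it is 0.2 to 16 points. The top of that range needs every discharged survivor to be called late.

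**Effect on the test.** Simulation of 1,500 trials per setting, 194 per arm, unstratified log-rank at two-sided 5%, comparing Day 29 censoring with the literal rule:

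| Assumptions | Hazard ratio | Rejection rate |
|---|---|---|
| Mortality 16% vs 8%; discharged 60% vs 72%; 10% of deaths late; 80% called late | 0.51 to 0.52 | 68% to 66% |
| As above, 15% of deaths late; 100% called late | 0.51 to 0.53 | 67% to 62% |
| Mortality 16% in both arms; discharged 65%; 10% of deaths late; 80% called late | 1.03 to 1.03 | 5.5% to 5.4% |

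**The case against.** A reader might infer that the SAP requires censoring at the Day 22 call and that Kaplan-Meier mortality will therefore be overstated. The documents do not support that, for four reasons.

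- The limit to Day X does not by itself rule out a later contact. The K-point improvement rule carries the same limit, "censored at the date of the last NIAID 8-point ordinal scale assessment on/before Day X", yet the example for that type of endpoint does not fall back to Day 22. The authors' intention appears to be the opposite.
- SAP 4.2.4 can be read as fixing one date, Day 31 in the example, which the overall-survival sentence then caps at Day 29. That is the protocol rule. On that reading there is no departure, and Section 6 has nothing to list.
- SAP 4.2.4 counts any dated record, such as an adverse event or medication date. Even on the literal reading the fallback may be later than Day 22.
- Call timing, discharge share and the share of late deaths are not in the documents. Calls are scheduled for Day 29 itself, so a high share of late calls is an assumption.

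The inferential weight is also low. Overall survival is tested last, and only if both doses succeed in the three families before it. Mortality is formally tested as a binary endpoint under a rule that handles the Day 31 contact correctly. The Kaplan-Meier mortality rate is supportive only.

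All of this stands, and it reduces the point to one of wording. It does not remove it. The window provision speaks of NIAID scores and last assessments, whereas the overall-survival rule uses the last date known alive, so it is not clearly covered. The Phase 2 SAP has the same overall-survival sentence, but its section 5.7.3 put the target day in place of the actual day for late in-window assessments. The Phase 3 SAP dropped that clause. Even if the Phase 3 provision is extended to overall survival, its example points to the actual contact day, which is not the protocol's Day 29.

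**Conclusion.** The point holds as a minor one. The Phase 3 overall-survival sentence is ambiguous. Its literal reading conflicts with protocol 10.2 and with SAP 5.7.2, and SAP Section 6 lists no such change, although it does list another change to censoring.

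If the literal reading is programmed, Kaplan-Meier mortality at Day 29 is biased upward: 18.9% against 16.0% in the illustration. That size depends on assumed deaths on Days 23 to 29, assumed late calls, and no other dated record after Day 22. There is no such excess if no death falls on those days, or if these subjects are censored at Day 29 or at the actual contact day.

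The hazard ratio moves by about 0.01 to 0.02, and with equal arms the rejection rate stays near 5%. A reader might go further and conclude that the overall-survival test is invalid or that the treatment comparison is materially distorted; these results do not support that. What is at risk is the reported survival curve and the supportive Day 29 estimate.

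**What to change.** Replace the overall-survival censoring sentence in Phase 3 SAP 5.7.3 with: *Subjects not known to have died by Day X are censored at the earlier of the last date known alive (using all contacts in the locked database, including those after Day X) and Day X.*

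This restores protocol 10.2 for every subject with a contact on or after Day 29, and for those subjects it agrees with SAP 5.7.2. Subjects with no such contact are still censored at their last date known alive.

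One clause should tie this to SAP 4.6. At the first database lock, Day 29 efficacy endpoints use data through the +4-day window, so the SAP should say whether contacts after Day 33 count at that lock or only at the second.

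The cost is one sentence, that clause and a line of programming. No new data are needed.
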